Cover Page

Study Title

“Implementation of a Shared Decision-Making Aid for Reducing Stigma against Drug Use and HIV Harm Reduction in a Rural Setting”

Identifiers: NCT05352412

Unique Protocol ID: 202107155

Date: March 25, 2022

Study Protocol

Project Title:

Implementation of a Shared Decision-Making Aid for Reducing Stigma against Drug Use and Harm Reduction in a Rural Setting

Select how you plan to obtain consent:

- Letter or information sheet with no signature
- Script for use either in person or over the phone with no signature

Summary:

Patients who inject drugs are at high risk for invasive bacterial and fungal infections related to contaminated needles. These patients should be treated with a combination of antibiotics and addiction treatment. Our team has demonstrated that medications for opioid use disorder (MOUDs; e.g., methadone, suboxone), improve patient outcomes. However, there is substantial stigma associated with these medications. Both patients and healthcare providers view them as drugs for "addicts." The goal of this proposal is to determine if a shared decision aid to help patients select the most appropriate MOUD will reduce internal stigma by the patient (reluctance to start on MOUDs) and stigma from the healthcare provider to offer a prescription for MOUDs. We propose to use serial stigma survey assessments before, directly after, and weeks after use of the tool.

Specify your research question(s), study aims or hypotheses:

We hypothesize that the use of the tool will reduce healthcare and patient stigma about use of MOUDs.

Background and significance and/or Preliminary studies related to this project:

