After Alpha and beta testing are completed in Aim 1 of this project: After the patient meets with a member of the Bridge To Health team, they will be referred to a member of the research team. The research team member will approach the patient and their provider of medication-assisted treatment once the patient has been stabilized to determine the patient's interest in treatment for their opioid use disorder, but prior to discharge from the hospital. This will usually occur within 2 weeks of the patient being discharged from the hospital. If a patient is interested in participating, consent will be obtained from the patient and their healthcare provider will be approached for consent as well. Once consent from both parties, patient and provider, is obtained the patient will be randomized to either receive the shared decision aid or standard of care. If randomized to receive the shared decision aid, the patient and provider will take the survey on separate devices but at the same time. The decision aid survey integrates a values clarification exercise and summarizes patient concerns/preferences to guide shared decision-making with clinicians. We will measure stigma and other outcomes prior to discharge, 2 weeks post-discharge, and 3 months post-discharge to assess the feasibility and preliminary effectiveness of the decision aid. If the patient is not randomized to receive the decision aid tool, they will complete the survey and receive standard of care. We will measure stigma and other outcomes prior to discharge, 2 weeks post-discharge, and 3 months post-discharge to assess the feasibility and preliminary effectiveness of standard of care.

We will implement a method to create a unique patient ID code to link participant data and information to rather than their name, and that the study team will not collect or record any identifiable health information in order to protect participants' confidentiality

What have you done to minimize any risks?

- Adverse event monitoring

What are the potential benefits related to this project for:

The patient will have more input on what type of MOUD they will receive. This might increase adherence.

The tool may help reduce stigma and improve long-term MOUD acceptance, which will reduce overdose rates among persons who inject drugs.

Provide a summary of the analysis methods you will use, including, if applicable, the data points or outcomes you will analyze.

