We will use likert scale questions to assess stigma immediately before and after the survey. We will also measure long-term stigma changes compared to baseline at 2 weeks and 3 months. These results will be compared to the baseline testing results in a paired manner. We will use non-parametric tests to evaluate for statistical significance. We will also compare overall response rates between those who did vs. did not receive the clinical decision tool.

Provide the rationale or power analysis to support the number of participants proposed to complete this study.

This is a pilot study. No power analyses needed.

Participants

18 years old. No age limit. We will not recruit non-English speaking people. Must have diagnosis of opioid use disorder and come from a rural location.

Sites:

Barnes-Jewish Hospital

Privacy and Confidentiality:

Only minimum necessary information to be collected. Recruit in a private setting when possible. Materials will be stored in a secured environment and team members will be the only ones with access.

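### The stigma score is tested only against baseline within participants; no comparison between the randomised arms is stated

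*Combined protocol and SAP*

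**What the plan says.** The section on research questions and hypotheses attributes the effect to the tool: "We hypothesize that the use of the tool will reduce healthcare and patient stigma about use of MOUDs". The study-procedures section sets up a randomised comparison, in which "the patient will be randomized to either receive the shared decision aid or standard of care", and gives both arms the same measurement times: before discharge, then 2 weeks and 3 months after it.

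That section describes the purpose of measurement one arm at a time. For the aid arm it is "3 months post-discharge to assess the feasibility and preliminary effectiveness of the decision aid"; for the control arm it is "3 months post-discharge to assess the feasibility and preliminary effectiveness of standard of care".

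The summary of analysis methods has Likert items answered around the survey, and then: "We will also measure long-term stigma changes compared to baseline at 2 weeks and 3 months". The analysis follows: "These results will be compared to the baseline testing results in a paired manner". Next comes "We will use non-parametric tests to evaluate for statistical significance", with no test named. The last sentence is the only one that sets the groups against each other: "We will also compare overall response rates between those who did vs. did not receive the clinical decision tool". The power-rationale section calls the study a pilot and gives no sample size.

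**The concern.** A paired comparison with baseline uses each participant as his or her own control. It removes stable differences between people, but not change over time that would have happened anyway. Such change is plausible here. Patients are recruited as inpatients with an infection and followed to 3 months after discharge. All have met the Bridge to Health team and agreed to discuss medication, and all answer the same stigma items repeatedly. The control arm is there to remove this change, but the written stigma analysis does not use it.

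An analyst could follow the plan exactly and report a significant fall in the aid arm as support for the hypothesis when the same fall occurred under standard of care. Testing each arm separately and noting that only one is significant does not repair this, because the difference between a significant and a non-significant result is not itself tested.

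**Working it through.** **1. Inputs from the documents.** Two arms, patient randomised, allocation ratio not stated; stigma on Likert items; follow-up at 2 weeks and 3 months; paired analysis; unnamed non-parametric tests. Sample size, alpha, SD, correlation and expected change are not given, so there is no figure of the plan's own to reproduce.

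**2. The texts side by side.**
- Hypothesis: a causal effect of the tool.
- Procedures: a randomised contrast is available, but each arm's assessment is described separately.
- Analysis: stigma against baseline, paired. The between-group sentence concerns response rates. Response could mean survey completion, the Likert answers, a responder category or medication uptake; the text does not say which.

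**3. What each analysis estimates.** Let τ be the effect of the aid and δ the change common to both arms.
- Expected change, aid arm: τ + δ
- Expected change, control arm: δ
- Difference between arms: (τ + δ) − δ = τ

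The paired analysis of the aid arm estimates τ + δ at any sample size. Only the between-arm difference isolates τ.

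**4. Illustration with no tool effect (τ = 0).** All inputs are assumed: two-sided 0.05; 15, 20 or 30 per arm; Likert sum with mean 32 and SD 6, rounded and bounded at 10–50; 4,000 simulated trials per cell (Monte Carlo SE at most √(0.5 × 0.5 / 4,000) = 0.8 percentage points). At baseline–follow-up correlation 0.5:

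| Common change δ | n per arm | Aid-arm signed-rank test significant | Aid arm significant, control not |
|---|---|---|---|
| 0.3 SD | 15 | 18% | 15% |
| 0.3 SD | 20 | 24% | 19% |
| 0.3 SD | 30 | 34% | 22% |
| 0.5 SD | 15 | 41% | 23% |
| 0.5 SD | 20 | 54% | 25% |
| 0.5 SD | 30 | 75% | 19% |

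The last column should be close to p(1 − p), where p is the third column, because the arms are independent: 0.24 × 0.76 = 0.18 and 0.54 × 0.46 = 0.25, which agree.

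Over correlations 0.3, 0.5 and 0.7 and all three sample sizes, the aid-arm test rejects in 4.3–5.1% of trials with no common change, 14.8–51.0% at 0.3 SD and 31.4–91.5% at 0.5 SD. Between-arm tests stay near 5% in all 27 null cells: ANCOVA 4.3–5.9%, rank ANCOVA 4.5–5.7%, Mann-Whitney on change scores 4.3–5.6%.

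A simpler simulation with normal change scores of SD 1 agrees. At n = 20 the aid-arm test rejects in 24.4% (δ = 0.3) and 54.0% (δ = 0.5), and Mann-Whitney on change scores in 5.5% and 5.4%.

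**5. Illustration with a real effect.** With τ = 0.5 SD and δ = 0.3 SD, the aid-arm change should average 0.5 + 0.3 = 0.8 SD. The simulation gives 0.79–0.80 SD; the ANCOVA difference averages 0.49–0.50 SD.

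**6. Price of the between-arm estimate.** With equal variances and correlation ρ, the SE of the within-arm change is SD × √(2(1 − ρ)/n). The SE of the ANCOVA difference is about SD × √(2(1 − ρ²)/n). Their ratio is √(1 + ρ): 1.14, 1.22 and 1.30 for ρ = 0.3, 0.5 and 0.7. The simulated CI ratios, which include small-sample t quantiles, are 1.12–1.29. For an unadjusted difference in change scores the ratio is √2 = 1.41; simulated, 1.36–1.39.

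At ρ = 0.5 the mean 95% CI half-widths for n = 15/20/30 are 0.66/0.56/0.45 SD (ANCOVA), 0.74/0.64/0.52 SD (difference in change scores) and 0.55/0.46/0.37 SD (within arm). Power for τ = 0.5 SD with no common change is 31/42/60% (ANCOVA), 30/39/57% (rank ANCOVA) and 24/33/46% (Mann-Whitney on change), against 42/54/74% for the paired test in the aid arm.

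**The case against.** The strongest reply is that a between-group comparison is there. The only instrument named in the analysis summary is the stigma survey, so the response-rate sentence may mean the stigma answers. An identical schedule in both arms makes most sense if they are to be contrasted, and the one-arm-at-a-time wording may only reflect a form that asks for procedures in sequence. This reading is possible and limits confidence. But the text does not link response to the stigma score, and if the reading is right, one sentence would settle the matter.

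The study is also a pilot claiming only preliminary effectiveness. That excuses the missing power analysis and softens the point. It does not explain leaving out the randomised contrast while planning significance tests.

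The percentages rest on assumed common change; with none, the paired test holds its level. That stands. So does the observation that the documents never propose concluding from one significant and one non-significant arm; those figures only show why that would not be a remedy. The simulations also assume independent patients, complete data and one follow-up, so they do not address patients sharing a provider or loss by 3 months.

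Two practical points stand as well. The decision aid is itself described as a web-based survey, and control patients are said to complete the survey; if that is the same one, a between-arm test would not isolate the aid. And a pre-randomisation baseline is not stated. Both need clarifying, but neither makes the paired test an answer to the hypothesis.

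**Conclusion.** The point holds and should be fixed. As written, the significance test on stigma asks whether scores moved from baseline, while the hypothesis asks whether the tool moved them. That conclusion follows from the text and the algebra and needs no assumed number. Its practical size depends on how much stigma would change without the aid, about which the documents are silent: negligible inflation if there is no common change, and roughly a one-in-five to three-in-four chance of a misleading significant result for 0.3–0.5 SD of common change at correlation 0.5 and 15–30 patients per arm. Confidence is medium because the response-rate sentence might have been meant to cover the stigma answers.

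**What to change.** Change the summary of analysis methods as follows.

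- Make the test of the hypothesis a comparison, between arms as randomised, of the patient stigma score at 2 weeks and at 3 months, adjusted for a baseline score taken before randomisation. State which time point leads.
- Use ANCOVA, or rank ANCOVA to stay with the non-parametric intention. Mann-Whitney on change scores is acceptable but less precise.
- Report the arm difference with a 95% CI, which suits a pilot.
- Keep paired within-arm changes as description, and draw no conclusion from one arm being significant and the other not.
- Replace the response-rate sentence with a named, defined outcome compared by randomised arm.
- Say which survey control patients complete.
- Specify the provider analysis once the study-population text, which has both populations randomised, is reconciled with the procedures text, which has only the patient randomised.

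For patients at 2 weeks and 3 months this is a change of wording, since both arms are already measured then. If the baseline is currently taken after randomisation, its timing must also move. The statistical cost is the wider interval and lower power shown above, and the result may look less favourable; the paired test's higher power is for a different question.

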Study population: We will have 2 study populations. Patients who receive MOUDs and healthcare providers who prescribe MOUDs. These populations will be randomized to either receipt or no receipt of the shared decision tool.

Recruitment: We will send an email to healthcare providers who prescribe MOUDs in the hospital. This will likely include addiction medicine services, internists, emergency medicine providers, psychiatrists, and infectious diseases physicians. We will send the email to people in these divisions. We will also notify staff in the Washington University Bridge to Health Program via email. These individuals include a case manager and 2 health coaches who care for persons who inject drugs as part of a quality improvement project. If these individuals identify a suitable candidate, they will contact our study coordinator or the PI that it is acceptable to approach the healthcare provider and/or patient for study recruitment. The study coordinator will discuss the study either in person or over the phone with the healthcare provider and in person with the patient. The study coordinator will discuss the risks and benefits of enrolling in the study and consent the patient.

Time to consider participation: patients and healthcare providers will have as much time as they need to consider participation. However, ideally, they should start this intervention prior to initiating a MOUD in the hospital.

Minimize coercion: our study coordinator is a trained staff therapist who will inform the participant that the study is completely voluntary and participation will not impact clinical care.

Provide a detailed description in sequential order of the study procedures following the consent process - DO NOT cut and paste from the Consent Document.

This decision aid is a web-based survey that is presented on a tablet. It includes five sections: (D1) Provide an overview of both the disease and treatment. (D2) Assess the patient's eligibility for pharmacotherapy. (D3) Compare the current medication options (methadone, buprenorphine, and long-acting naltrexone), examining demand characteristics, such as side effects, route of administration, and cost. (D4) Describe expectations for treatment duration and effects if the medication is self-discontinued. (D5) Complete a brief values clarification exercise.

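### Stigma change is tested for significance in two populations at three time points, with no primary comparison named and no between-arm test of stigma

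*Combined protocol and SAP*

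**What the plan says.** The single hypothesis covers two groups: "We hypothesize that the use of the tool will reduce healthcare and patient stigma about use of MOUDs". The enrolment section confirms them: "We will have 2 study populations. Patients who receive MOUDs and healthcare providers who prescribe MOUDs". The procedures section sets up a randomised comparison, in which "the patient will be randomized to either receive the shared decision aid or standard of care", and collects stigma in the control arm at the same follow-up points, there described as "to assess the feasibility and preliminary effectiveness of standard of care".

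The analysis-methods section gives three contrasts with baseline. The first is short-term: "We will use likert scale questions to assess stigma immediately before and after the survey". The other two are later: "We will also measure long-term stigma changes compared to baseline at 2 weeks and 3 months". The method is "These results will be compared to the baseline testing results in a paired manner", followed by "We will use non-parametric tests to evaluate for statistical significance". One further sentence compares response rates between those who did and did not receive the tool, without defining the term.

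The documents give no primary outcome, population, time point, alpha, sidedness or multiplicity rule. They do not say whether the paired tests are run in each arm, in the aid arm only, or with the arms pooled. The sample-size section says that the study is a pilot and gives no power analysis.

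**The concern.** One hypothesis is served by several tests of equal standing, and nothing says which of them answers it. If patients improve at 2 weeks but not at 3 months, or providers improve and patients do not, the plan offers no rule for what to conclude. Any favourable aid-arm result below the threshold could then be presented as support, at an error rate well above that of a single test.

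The second problem lies in the kind of test. Stigma may change between admission and follow-up for reasons unrelated to the tool, such as recovery, contact with the care team or repeated questioning. A paired test within one arm, or across both arms pooled, cannot separate these from an effect of the tool. The randomised control arm can, but the plan states no between-arm comparison of stigma change.

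**Working it through.** The plan states no sample size, alpha or error rate, so it has no figure to reproduce. The check asks how far the chance of a false positive rises under the plan as written.

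**Inputs**
- Populations: 2 (enrolment section).
- Contrasts with baseline: 3 (analysis-methods section).
- Arms: 2 (procedures section).
- Alpha: assumed two-sided 0.05, because none is stated.

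**Number of tests**
- Aid arm only, or arms pooled: 2 × 3 = 6.
- Each arm separately: 2 × 3 × 2 = 12.
- Both readings fit the text.

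**Independent tests**, chance of at least one false positive = 1 − (1 − α)^k
- k = 6: 1 − 0.95^6 = 26.5%.
- k = 12: 1 − 0.95^12 = 46.0%.
- In the direction of lower stigma only (0.025 per test), k = 6: 1 − 0.975^6 = 14.1%.
- For 12 tests at other alphas: 11.4% at 0.01 and 71.8% at 0.10.

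**Shared baseline.** The three change scores in a group share one baseline, so they are correlated. If all visits have the same variance s² and the same pairwise correlation r, each change has variance 2s²(1 − r) and two changes have covariance s²(1 − r). Their correlation is therefore 0.5. The chance P that at least one of three such tests rejects was simulated with 1,000,000 draws of three equicorrelated normal statistics. Groups (population, or population by arm) were taken as independent, so 6 tests give 1 − (1 − P)² and 12 tests give 1 − (1 − P)⁴.

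| Correlation | P, 3 tests | 6 tests | 12 tests | 6 tests, reduced stigma only |
|---|---|---|---|---|
| 0 (formula) | 14.3% | 26.5% | 46.0% | 14.1% |
| 0.3 | 13.6% | 25.4% | 44.3% | 13.2% |
| 0.5 | 12.5% | 23.5% | 41.5% | 12.1% |
| 0.7 | 10.9% | 20.6% | 37.0% | 10.6% |
| 0.9 | 8.4% | 16.0% | 29.5% | 8.2% |

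Example at 0.5: 1 − (1 − 0.1254)² = 23.5%.

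**Check with a non-parametric test.** Wilcoxon signed-rank tests were run on simulated continuous scores with a shared baseline and change-score correlation 0.5, using 10, 20 and 40 participants per group and 1,000 replicates each. They gave 39.5–40.0% for 12 tests and 21.0–21.6% for 6, close to the table.

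**Benchmark.** One prespecified two-sided test at 0.05 has a 2.5% chance of a false finding in the favourable direction. The six aid-arm tests at correlation 0.5 have 12.1%, and 12.1 / 2.5 is about 4.8 times as much.

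**The case against.** A reader might infer that 12 tests are planned and that a false positive is therefore close to an even chance. The documents do not support that:
- The figure of 12 requires separate paired tests in each arm, which the analysis section does not state.
- The 46% also requires full independence and counts results in either direction. An even chance would need ln 0.5 / ln 0.95 = 13.5 independent tests.
- In the 12-test reading, six tests fall in the standard-of-care arm, and a change there cannot be reported as an effect of the tool. Nor can a significant rise in stigma in the aid arm support the hypothesis. So it is not true that any of the 12 could carry the claim.
- Even the immediate contrast in the control arm is uncertain. The aid is itself described as a web-based survey, and the control-arm text lists measurements before discharge, at 2 weeks and at 3 months.

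The simulated figures also treat the groups as independent, although patients are enrolled with their providers and one provider may serve several patients. Positive correlation between groups would lower the chance of any false positive, provided that each test is valid.

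The pilot label is a further objection, since strict type I error control carries less weight in a pilot. A reader might also infer that a chance finding would decide whether a larger trial goes ahead, but the documents mention no larger trial.

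All of this limits the size of the problem. It does not remove it: the pilot label is used only to excuse the missing power analysis, while the analysis section still proposes to declare significance. Naming the comparison that answers the hypothesis is a different matter from correcting alpha.

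**Conclusion.** The point holds in a limited form and is a cheap improvement to the plan. No primary population, time point or contrast is named, and the randomised arms are not compared on stigma.

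At an assumed two-sided 0.05, the chance of at least one false positive is about 16–26% for 6 tests and 30–46% for 12, over correlations from 0.9 down to 0. The figure closest to a wrong conclusion about the tool is a false finding of reduced stigma in the six aid-arm tests: about 12–14% for correlations from 0.5 to 0, falling to 8% at 0.9, against 2.5% for one prespecified test.

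These figures assume that stigma does not change for any reason. If it drifts downward in both arms, paired tests within an arm will reject more often, and correcting for multiplicity would not help. The number of tests could also exceed 12, because the plan names no summary score and each Likert item might be tested separately.

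**What to change.** Before any outcome data are seen, name one between-arm primary comparison. An example is aid versus standard of care in patient stigma score at 3 months, adjusted for baseline, with the score defined and the alpha stated. A rank-based analysis of covariance would keep the non-parametric intent. Report the provider, immediate, 2-week and within-arm contrasts as exploratory estimates with 95% confidence intervals and no claim of significance. With a single primary comparison, no alpha correction is needed.

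This takes a few sentences in the analysis section. It needs no extra participants or visits, because stigma is already to be measured in both arms at 3 months. There are two costs. Significance on the other contrasts can no longer be offered as confirming the hypothesis. A between-arm difference is also less precise than a within-arm change: with equal arms and equal variances, its standard error is √2 = 1.41 times that of one arm's mean change, although baseline adjustment recovers part of this. That is the price of an estimate that can be attributed to the tool.

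### The only between-group comparison is worded by receipt of the tool, and nothing in the plan says that participants are analysed by randomised arm

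*Combined protocol and SAP*

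**What the plan says.** All of the analysis text is in the protocol's summary of analysis methods. Stigma is measured around the survey and again at 2 weeks and 3 months, and of the later results it says "These results will be compared to the baseline testing results in a paired manner". The testing is described only as "We will use non-parametric tests to evaluate for statistical significance". The single comparison between groups is "We will also compare overall response rates between those who did vs. did not receive the clinical decision tool".

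Allocation is described in two other places. The study-population paragraph of the enrolment and consent section says "These populations will be randomized to either receipt or no receipt of the shared decision tool", where the populations are patients and providers. The study-procedures section, after consent from both parties, says "the patient will be randomized to either receive the shared decision aid or standard of care". For those allocated to the aid, it adds that "the patient and provider will take the survey on separate devices but at the same time".

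The document does not say how to treat someone allocated to the aid who does not receive it. It names no analysis set. On sample size it says only "This is a pilot study. No power analyses needed".

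**The concern.** Receipt of the aid comes after randomisation. It depends on the patient and the provider both being available and willing at the same moment, before discharge. Some patients allocated to the aid may never get it. An analyst who follows the comparison sentence word for word would count them with those who did not receive the tool, alongside the control arm.

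The two groups would then no longer be the groups that randomisation made comparable. If those who miss the aid differ in how they would have responded anyway, a difference can appear when the aid does nothing. This matters because the sentence is the plan's only use of the randomised control group. The stigma analysis as written compares people with their own baseline.

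**Working it through.** **No figure to reproduce.** The document gives no sample size, alpha, allocation ratio, response rate or rate of non-receipt. Everything numerical below is an assumption, used only to show how the wording could matter.

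**Reading the text.**
- Both allocation sentences attach the word randomised to receiving or receipt. The analysis sentence drops it and uses the past tense. Literally, that is actual receipt.
- Receipt is not defined. The procedures call the aid a web-based survey, yet also say that patients not allocated to it complete the survey.
- The term response rates is not defined either. It could mean return of the follow-up survey or a stigma response.

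**Illustration.** Assume 1:1 allocation, no true effect, and a share *q* of the aid arm that does not receive the aid. Would-be receivers respond at *pc* and non-receivers at *pn*, with the same mix in the control arm.

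- By randomised arm, both arms respond at (1−q)·pc + q·pn, so the expected difference is 0.
- By receipt, the receivers respond at pc. The others respond at [(1−q)·pc + 2q·pn]/(1+q).
- The false gap is therefore 2q(pc − pn)/(1+q).

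With q = 0.20, pc = 0.75, pn = 0.40:
- each arm as randomised: 0.8×0.75 + 0.2×0.40 = 0.68
- those not receiving: (0.68 + 0.2×0.40)/1.2 = 0.633
- false gap: 0.75 − 0.633 = 0.117, about 12 points

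With the same response rates, q = 0.10 gives 0.07/1.1 = 6.4 points and q = 0.30 gives 0.21/1.3 = 16.2 points.

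**Other assumed values, pc = 0.70:**

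| pn | q = 10% | q = 20% | q = 30% |
|---|---|---|---|
| 0.70 | 0 | 0 | 0 |
| 0.50 | +3.6 | +6.7 | +9.2 |
| 0.30 | +7.3 | +13.3 | +18.5 |
| 0.90 | −3.6 | −6.7 | −9.2 |

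(Percentage points, receivers minus the rest.)

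**Chance of a false significant benefit.** This uses a pooled two-proportion normal approximation at two-sided 5% (2.5% in the favourable direction), with group sizes n(1−q) and n(1+q). At q = 20%, pc = 0.70, with assumed n of 20, 50 and 100 per arm:
- pn = 0.50: about 6%, 10% and 16%
- pn = 0.30: about 13%, 26% and 48%

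If pn = pc, or if q = 0, it stays at 2.5%. Analysed by randomised arm, it stays at 2.5% for any pn and q.

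**The case against.** The strongest reply is that receiving the tool is simply how this protocol names its arms. The study-population paragraph calls the allocation receipt or no receipt, and the procedures use the same verb. On that reading the comparison sentence already means the randomised arms. This is plausible, so the sentence cannot be called a decision to abandon randomisation. What stands is that the sentence omits the reference to randomisation, and no other text rules out the literal reading.

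A reader might also infer that patients who do not complete the aid are moved into the comparator. The document contains no such rule. It speaks of receiving, not completing, so someone who starts the aid and stops may still count as having received it.

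A reader might further infer that the bias must favour the aid, because reluctant patients would be the ones to miss it. That is not established. Patients must already be willing to discuss these medications with a provider, and both parties consent before randomisation. Non-receipt could reflect provider scheduling as easily as reluctance. The bias could be zero or run the other way, as the table shows.

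Finally, one could compute a bias in stigma scores in standard-deviation units. The plan describes no between-arm comparison of stigma, so such a figure would not follow from its text.

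Pilot status is a fair reason for modest severity. It does not remove the point, because the protocol intends an early look at effectiveness and plans significance tests.

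**Conclusion.** The concern holds as an ambiguity with a consequence. The plan's one between-group comparison is literally by receipt, and nothing states that participants are analysed as allocated. If the literal reading is followed, and non-receipt after randomisation is related to outcome, the comparison is biased.

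Neither the size nor the direction can be taken from the documents. The 12-point gap rests on assumed 1:1 allocation, 20% non-receipt, and 75% against 40% response. Other assumed inputs give anything from a gap against the aid, through zero, to +18.5 points. The documents do not support saying that the plan reassigns non-completers or that its result will be tilted towards the aid. The plan should be clarified before analysis.

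**What to change.** Replace the receipt phrase in the analysis summary with: *those randomised to the decision aid vs. those randomised to standard of care, all randomised participants with data analysed in their allocated arm whether or not they received or completed the aid*.

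Also:
- Define response rates. If survey return is meant, the denominator is everyone randomised.
- Compare change in stigma from baseline between the same randomised arms with a non-parametric test, since the plan otherwise gives only paired within-person comparisons. This is an added analysis, using data already to be collected.
- Reconcile the study-population paragraph with the study-procedures section on whether providers are randomised, and group providers accordingly.
- Report receipt and completion of the aid descriptively, as feasibility results. Label any by-receipt analysis secondary.

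The cost is a few sentences and no new data. The price in estimation is some dilution. If the aid has no effect in those who miss it, and 20% of the aid arm miss it, the by-arm difference is 1 − 0.20 = 80% of the effect among would-be receivers.
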